2.2.14 Concomitant Analgesic Medication Change Definitions

Concomitant analgesic medication use for each subject will be programmatically categorized from the eDiary data using the following definitions:

- (1) No change in the amount or strength of concomitant analgesic medications
 - For each concomitant analgesic medication the subject is taking at Baseline, the average daily dose change from Baseline to Week 12 is within 15% of the average daily dose in the 7 days prior to Baseline *and*
 - No new concomitant analgesic medications are started at any time after baseline until week 12 *and*
 - No concomitant analgesic medications are discontinued at any time after baseline until week 12
- (2) Decrease in the amount or strength of concomitant analgesic medications
 - For at least one concomitant analgesic medication the subject is taking at Baseline, the average daily dose change from Baseline to Week 12 has decreased by at least 15% of the average daily dose in the 7 days prior to Baseline *and*
 - For all other concomitant analgesic medication the subject is taking at Baseline, the average daily dose change from Baseline to Week 12 does not increase by >15% of the average daily dose in the 7 days prior to Baseline *and*
 - No new concomitant analgesic medications are started at any time after baseline until week 12 unless a non-opioid analgesic

medication is added and an opioid analgesic is discontinued (i.e., a non-opioid replaces an opioid analgesic medication as described below).

- (3) Increase in the amount or strength of concomitant analgesic medications
- For at least one concomitant analgesic medication the subject is taking at Baseline, the average daily dose change from Baseline to Week 12 is $>15\%$ of the average daily dose in the 7 days prior to Baseline *or*
 - A new concomitant analgesic medication is started at any time after baseline until week 12, unless a non-opioid analgesic medication is added and an opioid analgesic is discontinued (i.e., a non-opioid replaces an opioid analgesic medication as described below).

If any non-opioid analgesic is added but simultaneously (within two days) an opioid analgesic is permanently discontinued, this will not be considered an increase in the amount or strength of concomitant analgesic medications; instead, it will be considered a decrease.

A separate blinded assessment of concomitant analgesic use will be provided following a manual review. For this manual review, a charter will be prepared describing the process. Individuals with knowledge and training will review concomitant analgesic data from each individual subject and classify each subject as having a decrease, no important change, or an increase in concomitant medications. This assessment will be used in a separate analysis supportive of the programmatic assessment.

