8.11 Concomitant Medications

8.11.1 Permitted Medications

The use of stable concomitant therapy is allowed throughout the study, except for those medications prohibited in [Section 8.11.2](#). All concomitant medications must be recorded in the appropriate sections of the eCRF or the eDiary as appropriate, and updated if any changes occur. Concomitant medications should include all medications taken within 30 days prior to Screening Visit 1 and throughout the study.

The following medications are permitted for use during the study:

- Short-acting opioid or opioid-containing analgesics (e.g., acetaminophen + codeine) for treatment of pain, including CP/CPPS symptom flares but treatment per protocol is only

permitted for fewer than 5 days per week or no more than 10 doses per month

- Non-opioid-containing analgesics (e.g., acetaminophen)
- Non-steroidal anti-inflammatory drugs (NSAIDs) only if on a stable dose (i.e. stable pattern and frequency of use) for ≥ 30 days prior to Screening Visit 1
- Medications for treating diseases other than CP/CPSP are permitted, provided they are not included in the list of prohibited medications listed in [Section 8.11.2](#).
- Medications for treating CP/CPSP are permitted, provided they are not included in the list of prohibited medications listed in [Section 8.11.2](#), and the subject has been on a stable dose for ≥ 30 days prior to Screening Visit 1 and plans to continue current pattern of usage for the duration of the study.

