8.11.2 Prohibited Medications

The following medications are prohibited for use during the study:

- Any long-acting opioids
- Oral steroid therapy, immunosuppressants/immunomodulators (including daily phosphodiesterase type 4 inhibitors)

If a subject requires short-acting opioid analgesics for ≥ 5 days per week on >1 occurrence during the study or >10 times per month on >1 occurrence during the study, or require a prohibited medication to treat an AE, the subject may remain in the study. The use of the prohibited medication should be captured on the eCRF.

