10.4.2.4 Secondary Efficacy Endpoints

The secondary efficacy endpoints are:

- The change from Baseline to Week 12 for each of the following:
 - NIH-CPSI pain subscale and all domains total score
 - Male sexual health as measured using the IIEF-EF
 - Mean of average daily pelvic pain scores (eDiary), average and maximum daily pelvic pain (paper-based NRS in clinic)
 - 24-hour voiding frequency (eDiary)
- Time course of effects: AQX-1125 (200 mg once-daily) compared to placebo on the change from Baseline (Visit 2) to Week 6 (Visit 3), Week 12 (Visit 4), and Week 16 (i.e. 4 weeks after end of treatment) for each of the following:
 - Mean of maximum daily pelvic pain score (eDiary)
 - NIH-CPSI pain subscale and all domains total score
 - IIEF-EF
 - Mean of average daily pelvic pain scores (eDiary), average and maximum pelvic pain (Paper-based NRS in clinic).
 - 24-hour voiding frequency (eDiary)
- Response to treatment as measured by the GRA, PGI-C, and PGI-S at Week 12 (Visit 4).

- A $\geq 30\%$ and $\geq 50\%$ improvement in maximum daily pelvic pain (using the 11-point NRS recorded by eDiary and the NIH-CPSI pain subscale) compared to placebo, at Week 6 (Visit 3) and Week 12 (Visit 4).
- Responder analysis: Response to treatment defined by any of the following:
 - Decrease in maximum daily pelvic pain from Baseline to Week 12 (eDiary) with no change in the amount or strength of concomitant analgesic medications
 - Decrease in maximum daily pelvic pain from Baseline to Week 12 (eDiary) with a decrease in the amount or strength of concomitant analgesic medications
- Discontinuation of study medication due to treatment failure (% meeting treatment failure criteria and time to event)

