10.4.2.5 Secondary Efficacy Endpoints Analyses

For the following dichotomous secondary efficacy endpoints, the rates for each treatment group and the difference between the treatment groups will be presented with corresponding 95% CIs. A Cochran–Mantel–Haenszel test will be used to test for differences in rates between the treatment groups controlling for baseline pelvic pain.

- Treatment response as defined by meeting either of the following:
 - Decrease in maximum daily pelvic pain from Baseline to Week 12 using a standardized 11-point NRS with no change in the amount or strength of concomitant analgesic medications
 - Decrease in maximum daily pelvic pain from Baseline to Week 12 using a standardized 11-point NRS with a decrease in the amount or strength of concomitant analgesic medications
- A $\geq 30\%$ and $\geq 50\%$ improvement in maximum daily pelvic pain (using the 11-point NRS recorded by eDiary and the NIH-CPSI pain subscale), at Weeks 6 (Visit 3) and 12 (Visit 4).
- Discontinuation of study medication due to treatment failure (% meeting treatment failure criteria and time to event)

The following change from Baseline to Week 12 endpoints will be analyzed in a manner similar to the primary efficacy analysis as described in [Section 10.4.2.3](#).

- NIH-CPSI pain subscale and all domains total score.
- Male sexual health as measured using the IIEF-EF.
- Mean of average daily pelvic pain scores (eDiary), daily pelvic pain (in clinic), and maximum daily pelvic pain (in clinic).
- 24-hour voiding frequency

Additionally, for the IIEF-EF domain endpoint, the frequency distribution of the 5 category IIEF-EF score (i.e. described in [Appendix 5. International Index of Erectile Function Questionnaire](#)) will be presented by treatment group for Week 12 as well as a shift table from Baseline. Treatment group difference in the 5-category IIEF-EF will be assessed by a Cochran-Mantel-Haenszel (CMH) test controlling for Baseline IIEF-EF score.

The following time course secondary endpoints will be assessed by MMRM ANCOVA model where the change from Baseline is the dependent variable and linear trends across time (i.e., visit) are assessed.

Time course of effects: AQX-1125 (200 mg once-daily) compared to placebo on the change from Baseline (Visit 2) to Week 6 (Visit 3), Week 12 (Visit 4) and Week 16 (i.e. 4 weeks after end of treatment) for each of the following:

- Mean of maximum daily pelvic pain score (eDiary).

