 - Decrease in maximum daily pelvic pain (mean) from Baseline to Week 12 using a standardized 11-point NRS with no change in the amount or strength of concomitant analgesic medications (as defined in Section 2.2.14).
 - Decrease in maximum daily pelvic pain from Baseline to Week 12 using a standardized 11-point NRS with a decrease in the amount or strength of concomitant analgesic medications (as defined in Section 2.2.14).
- (2) A $\geq 30\%$ and $\geq 50\%$ improvement (decrease) in maximum daily pelvic pain (mean) (using the 11-point NRS recorded by eDiary and the NIH-CPSI pain subscale), at Weeks 6 (Visit 3) and 12 (Visit 4).

For the Discontinuation of study medication due to treatment failure endpoint, only summary statistics will be provided for the percent meeting treatment failure criteria and the time to event (no inferential analyses will be performed). Time to discontinuation of study medication due to treatment failure will be summarized and presented graphically using Kaplan-Meier methods (i.e., SAS PROC LIFETEST stratifying on treatment group).

The frequency distribution of the 5-category IIEF-EF score will be presented by treatment group for Week 12 as well as a shift table from Baseline. The 5 categories are no erectile dysfunction (score: 26-30), mild erectile dysfunction (score: 22-25), mild to moderate erectile dysfunction (score: 17-21), moderate erectile dysfunction (score: 11-16) and severe erectile dysfunction (score: 1-10). Responses to all items must be completed to calculate an IIEF-EF score. Any response with missing values will be excluded from the analyses. Treatment group difference

with corresponding 95% CIs in the 5-category IIEF-EF will be assessed by a Cochran-Mantel-Haenszel (CMH) test using row mean scores controlling for Baseline IIEF-EF score.

Data from both treatment arms will be used to calculate a meaningful change threshold (MCT), which reports a change in the primary endpoint (change in maximum daily pelvic pain) by anchoring to other outcomes (including PGI-S and/or PGI-C) to determine a change in maximum pelvic pain that provides a meaningful benefit to patients. The determination of the MCT will be made outside of the methods documented in this SAP prior to database lock. Once the MCT is determined, the proportion of subjects who have an improvement of at least the MCT will be summarized by treatment group and compared using a chi-square test as an exploratory analysis.

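### SAP 2.2.14 classifies analgesic change from the eDiary alone, so an analgesic recorded only on the eCRF can misclassify a man in the secondary responder analysis

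*SAP*

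**What the plan says.** - **Endpoint.** Protocol 10.4.2.4 gives two routes to response. One is "Decrease in maximum daily pelvic pain from Baseline to Week 12 (eDiary) with no change in the amount or strength of concomitant analgesic medications"; the other is the same fall in pain with a decrease in analgesics. The eDiary is named as the source of the pain score. No source is named for the analgesic condition.
- **Programming rule.** SAP 2.2.13.3 uses the same two routes and takes the analgesic categories from SAP 2.2.14, which says: "Concomitant analgesic medication use for each subject will be programmatically categorized from the eDiary data". One requirement for 'no change' is "No new concomitant analgesic medications are started at any time after baseline until week 12".
- **Where medications are recorded.** Protocol 8.11.1: "All concomitant medications must be recorded in the appropriate sections of the eCRF or the eDiary as appropriate". It does not say which analgesics belong in which record.
- **Prohibited medications.** Protocol 8.11.2 lists "Any long-acting opioids", allows a man who needs a prohibited medication for an adverse event to stay in the study, and adds: "The use of the prohibited medication should be captured on the eCRF".
- **What the eDiary should hold.** Protocol 6.1 and SAP 2.2.2 have each man enter his analgesics daily from screening to Week 16. Neither makes an exception for prohibited drugs.
- **Manual review.** SAP 2.2.14 ends with a blinded review of each man's analgesic data under a charter still to be prepared. It feeds a separate supportive analysis, and its data sources are not named.

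**The concern.** The analgesic condition is there to stop relief from added painkillers being counted as response to study drug. It can do this only if the programmed rule sees the added painkiller. The protocol keeps two medication records and the rule reads one of them. Where the two disagree, the choice of source, rather than what the man took, settles whether he is a responder. At stake is the accuracy of each arm's responder rate and, if disagreements are more common in one arm, the comparison between arms.

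**Working it through.** **1. Same drug use, different record.** Take a man whose mean maximum pain has fallen at Week 12 and whose other diary analgesics are unchanged, and apply SAP 2.2.14.

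| Actual use | Where recorded | Category from the eDiary | Result |
|---|---|---|---|
| Opioid started after Baseline | eDiary, with or without eCRF | Increase (the replacement exception covers only an added non-opioid) | Non-responder |
| Opioid started after Baseline | eCRF only | No change: nothing new, stopped or altered in dose | Responder |
| Analgesic in use at Baseline and continued | On the eCRF; absent from the diary in the baseline week, entered later | Increase, because it looks new (unless the replacement exception applies) | Non-responder |

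Row 2 is a false responder. Row 3 is a false non-responder. Both need the diary to omit a use that the eCRF holds.

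**2. Does another rule catch the omission?**
- SAP 2.2.10.1 handles missing days for weekly mean scores. SAP 2.2.14 has no rule for missing medication days, so an empty day can read as no analgesic taken.
- SAP 2.2.13.1 needs 4 pain entries in the 7 days before a visit. The test for new analgesics runs over the whole period from Baseline to Week 12. A man can therefore have a valid Week 12 pain value and gaps earlier in the period that the medication test covers.
- The protocol schedule has sites review the eDiary and, separately, concomitant medications at Weeks 6 and 12. A second record therefore exists, but the rule does not use it.

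**3. Arm size.** The plan gives a difference of 1.2, SD 2.0, two-sided 5% and 80% power.
- Normal approximation: n = 2 × (1.960 + 0.842)² × (2.0/1.2)² = 43.6, so 44 per arm.
- Two-sample t-test: 44.6, so 45 per arm, with power 80.4% at 45. This reproduces the plan.
- 90/(1 − 0.10) = 100 randomized, or about 50 per arm.

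The sample size itself is not in question; only the 50 per arm is used below.

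**4. Effect on one arm's rate.** One misclassified man: 1/50 = 2.0 points. Two: 4.0. Three: 6.0. Five: 10.0.

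**5. Effect on the comparison (illustration only).** The documents give no responder rates. Assume true rates of 40% on placebo and 60% on AQX-1125, 50 per arm, a two-sided 5% comparison of two proportions, and false responders only.

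| False responders, placebo v active | Observed difference | Power |
|---|---|---|
| 0% v 0% | 60 − 40 = 20 points | 52% |
| 4% v 2% | 62 − 44 = 18 points | 44% |
| 10% v 2% | 62 − 50 = 12 points | 22% |
| 10% v 10% | 70 − 50 = 20 points | 53% |

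Reversing the third row (2% placebo v 10% active) gives 70 − 42 = 28 points, an inflated difference. Balanced cases leave the difference at 20. With assumed rates of 30% v 50% or 50% v 70%, power at 10% v 2% is 22% and 24%.

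**The case against.** The strongest reply is that the eDiary is the protocol's designated daily analgesic record, so SAP 2.2.14 uses the right source. A reader might infer from protocol 8.11.2 that prohibited opioids go to the eCRF instead of the diary. The text does not say so: eCRF capture is an addition, and the daily diary entry has no exception. This stands, and it limits the point to uses that the diary omits.

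The route is also narrow. The only analgesics on the prohibited list are long-acting opioids, and men expected to take them are excluded at entry. Section 8.11.2 leaves unclear whether short-acting opioid use above its limits counts as prohibited use for eCRF capture. Opioid use continuing at Week 12 falls in a week with at least 4 pain entries, so the damaging case is mainly a man who enters his pain and leaves out the drug. That is fair as to frequency. It does not change what the rule does when the case occurs, and a start at any time after Baseline is enough to rule out 'no change'.

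Finally, the manual review and the concomitant-medication listings (SAP 2.2.15.5) could reveal discrepancies. They could, but the review's sources are unnamed, it is supportive only, and neither it nor the listings correct the programmed result.

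**Conclusion.** The point holds as a defect in a stated rule, of modest consequence. SAP 2.2.14 bases the analgesic category, and with it the responder endpoint, on one of two medication records, and no section reconciles them. A use recorded only on the eCRF can turn a non-responder into a responder or the reverse, at about 2 points of an arm's rate per man, assuming 50 per arm.

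Two stronger conclusions might be inferred, and the documents support neither. The first is that the error runs only towards false responders; the baseline-omission case runs the other way. The second is that the endpoint is biased by some stated amount. No frequency of eCRF-only records is given, so any number of points restates an assumed count, and the difference between arms shifts only if the cases are unbalanced.

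The endpoint is secondary with descriptive P values (SAP 2.2.13.3), and the primary analysis does not use the analgesic category.

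**What to change.** Amend SAP 2.2.14 as follows:

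1. Determine which analgesics were in use at Baseline, started, or stopped up to Week 12 from the eDiary and the eCRF concomitant-medication records combined. Apply this to baseline use as well as later starts, so that both directions of error are addressed.
2. Reconcile the two sources blind, before the unblinding that SAP 2.2.12 places after the Week 16 lock.
3. Keep the 15% average-daily-dose comparison on eDiary data where the eCRF has no daily doses; the documents do not show whether it has them.
4. State how conflicting records and missing diary medication days are handled.
5. Have the manual review use both sources, and say so in its charter.
6. Keep the eDiary-only classification as a sensitivity analysis.

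The cost is a change of SAP wording, a merge of two datasets already being collected, and some extra blinded reconciliation. No treatment or medication rule changes.

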
 • Short-acting opioid or opioid-containing analgesics: more than 10 doses/month, or more than a single dose > 2 days per week, or any short-acting opioid within 3 days prior to randomization • Oral steroid therapy, immunosuppressants / immunomodulators (including daily phosphodiesterase Type 4 inhibitors) within 30 days prior to Screening Visit 1 and throughout the study • Have taken any investigational drug or device within 90 days prior to Screening Visit 1, or have had previous exposure to AQX-1125 
15. Any prior history of pelvic cancer (e.g., colorectal, genitourinary) or treatment (radiation or chemotherapy) thereof
 
16. Major surgery within 3 months prior to Screening Visit 1
 
17. Have any other condition/disease which, in the opinion of the Investigator, could compromise subject safety or interfere with the subject's participation in the study or in the evaluation of the study results. In case of any doubt, the Investigator shall consult the medical monitor.
 
18. Known intolerance to micro-crystalline cellulose (Avicel® PH-102), mannitol or other ingredient of AQX-1125 tablets

Test Product, Dose and Mode of Administration:
 
Two AQX-1125 (activator of the Src homology 2-containing inositol-5'-phosphatase 1 protein) 100 mg tablets will be administered orally once daily with a glass of water, around the same time of day, for 12 weeks. Tablets should be taken with food or eat a light meal no more than 4 hours prior to consumption.

Reference Therapy, Dose and Duration of Administration:
 
Matching placebo is identical in appearance to the test product and contains no active ingredient. Two placebo tablets will be administered orally once daily with a glass of water, around the same time of day, for 12 weeks. Tablets should be taken with food or eat a light meal no more than 4 hours prior to consumption.

Duration of Treatment:
 
Subjects will participate in a 12-week, double-blind treatment phase. After the treatment phase, there will be a 4-week post last dose Safety Follow-up, as well as a 6-month post last dose Ophthalmic Safety Follow-up. There will also be a 3-month post last dose Telephone Call Follow-up.

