 - **Short-acting opioid or opioid-containing analgesics**: more than 10 doses/month, or more than a single dose > 2 days per week, or any short-acting opioids within 3 days prior to randomization
 - **Oral steroid therapy, immunosuppressants/immunomodulators** (including daily phosphodiesterase Type 4 inhibitors) within 30 days prior to Screening Visit 1 and throughout the study
 - Have taken any **investigational drug or device** within 90 days prior to Screening Visit 1, or have had previous exposure to AQX-1125
15. Any prior history of pelvic cancer (e.g., colorectal, genitourinary) or treatment (radiation or chemotherapy) thereof
16. Major surgery within 3 months prior to Screening Visit 1
17. Have any other condition/disease which, in the opinion of the Investigator, could compromise subject safety or interfere with the subject’s participation in the study or in the evaluation of the study results. In case of any doubt, the Investigator shall consult the medical monitor
18. Known intolerance to micro-crystalline cellulose (Avicel[®] PH-102), mannitol or other ingredient of AQX-1125 tablets

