8.4 Randomization

Randomization will be conducted at Baseline (Visit 2), after verifying that the subject meets all inclusion criteria and has none of the exclusion criteria. Approximately 100 male subjects with diagnosed CP/CPPS will be randomized to either AQX-1125 (200 mg) or placebo in a 1:1 ratio.

A central, permuted block randomization scheme will be used with a selected blocking factor (block size) determined based on the proposed allocation ratio and number of subjects.

An Interactive Web Response System (IWRS) will be used for the randomization to either AQX-1125 (200 mg) or placebo and subsequent wallet assignments. Study staff will log in to the IWRS using appropriate credentials and input subject-specific information (i.e. subject number and other basic identifiers). In accordance with the randomization schedule, the IWRS will assign the randomization number and the unique wallet numbers to the subject. Each subject must be given only the wallets assigned by IWRS. The study staff will document the wallet numbers in the Case Report Form (CRF). Subjects are to be randomized in the order in which they qualify from the screening phase for inclusion in the study.

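### The opioid-free days required at entry fall inside the baseline window for analgesic change, so many short-acting-opioid users with unchanged use are classed as increasing and counted as non-responders

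*SAP*

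**What the plan says.** Protocol 7.2, exclusion 14, makes a subject ineligible for "any short-acting opioids within 3 days prior to randomization". The Protocol synopsis has the same rule ("any short-acting opioid within 3 days prior to randomization") and the SAP synopsis repeats it. Protocol 8.4 fixes the timing: "Randomization will be conducted at Baseline (Visit 2), after verifying that the subject meets all inclusion criteria".

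The same exclusion caps usual short-acting-opioid use by barring "more than 10 doses/month, or more than a single dose > 2 days per week". After randomization, Protocol 8.11.1 allows these drugs; they are "permitted for fewer than 5 days per week or no more than 10 doses per month". Protocol 8.11.2 lets subjects who exceed the limits stay in the study. Neither section asks for opioid-free days before Week 12.

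SAP 2.2.14 sorts each subject by program, from the eDiary, into *no change*, *decrease* or *increase*. *No change* requires each analgesic taken at Baseline to be "within 15% of the average daily dose in the 7 days prior to Baseline" at Week 12, with nothing started or stopped. *Increase* is a rise above 15% in any baseline analgesic, or this event: "A new concomitant analgesic medication is started at any time after baseline until week 12". The only exception is a non-opioid that replaces an opioid. The same 7-day reference serves all analgesics.

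SAP 2.2.13.3 defines a responder as a subject whose maximum pain falls and whose analgesic category is *no change* or *decrease*. The end of SAP 2.2.14 adds a blinded manual classification, used only in a separate supportive analysis.

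**The concern.** Visit 2 is Day 1, so the opioid-free days are Days -3 to -1 and the reference window is Days -7 to -1. Entry empties three of the seven reference days of short-acting opioids, while the Week 12 days carry no restriction. The opioid reference dose is therefore biased downward, and 2.2.14 has no rule that corrects it.

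A man whose opioid use never changes can be classed *increase*. He then meets neither responder route, even if his pain has fallen. The same bias works against the route meant to credit pain relief with less analgesic, because a real cut in opioid use can also be read as a rise. What is at stake is the analgesic-adjusted responder rate in each arm and the difference between arms, both reported with 95% confidence intervals.

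**Working it through.** **Inputs from the documents.** Opioid-free days: 3 (Protocol 7.2). Reference window: 7 days, band 15% (SAP 2.2.14). Entry cap: 10 doses a month, which is 10 / (30.4/7) = 2.3 a week.

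**Assumptions.** Doses that would have fallen on Days -3 to -1 are skipped, not moved earlier. There is at most one dose a day. SAP 2.2.14 does not define the Week 12 averaging window, so I take 7 days. A subject with no opioid on the reference days who uses one later is classed *increase*, through the new-medication clause. The usage rates are assumed.

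The plan gives no figure for this endpoint. Its sample size of 45 per group reproduces (80.4% power by the two-sample t-test), but it concerns the primary endpoint and does not enter here.

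**1. Expected ratio under even, unchanged use.** Four of seven reference days are usable, so the Week 12/baseline ratio is 7/4 = 1.75, an apparent rise of 75%. A true cut of 30% reads as 0.70 × 1.75 = 1.225, still an *increase*. Reaching *no change* needs a true ratio of 1.15/1.75 = 0.657 (a 34% cut). Reaching *decrease* needs 0.85/1.75 = 0.486 (a 51% cut).

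**2. Fixed weekly pattern, all choices of weekday enumerated.**

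| Dosing days a week | Patterns | All doses on Days -7 to -4: *no change* | Some doses lost: *increase* | Zero baseline: *increase* |
|---|---|---|---|---|
| 1 | 7 | 4 (57%) | 0 | 3 (43%) |
| 2 | 21 | 6 (29%) | 12 (57%) | 3 (14%) |

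Total *increase* is 43% at one dosing day a week and 15/21 = 71% at two.

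**3. Random unchanged use, each day independent.**

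| Doses a week | *Increase*, 7 usable days | *Increase*, 4 usable of 7 | Added by the opioid-free days | *Decrease*, 7 usable | *Decrease*, 4 usable of 7 |
|---|---|---|---|---|---|
| 1 | 45.8% | 64.1% | 18 points | 34% | 20% |
| 2 | 39.2% | 61.4% | 22 points | 38% | 18% |
| 2.3 | 39.2% | 63.2% | 24 points | 39% | 17% |

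The 7-usable columns show the error that exists without any washout. With one or two doses, only an identical count stays inside a 15% band.

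**4. Sensitivity to the new-medication reading.** If a zero-baseline user is judged on Week 12 use alone, *increase* is 46%, 59% and 62% with the opioid-free days, against 34%, 38% and 39% without them. The added share is then about 12, 21 and 23 points.

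**5. Effect on the responder difference.** Let f be the share of opioid users (unknown), a the added share classed *increase* and e the share without the washout. Assume users' pain response matches that of others. The relative shrinkage of the difference is f·a / (1 − f·e).
- f = 10%: 0.0183/0.9542 = 1.9% at 1 dose a week; 0.0240/0.9608 = 2.5% at 2.3 a week.
- f = 30%: 0.0549/0.8626 = 6.4% and 0.0720/0.8824 = 8.2%.

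**The case against.** The strongest reply is that entry admits only light users. Their one or two weekly doses may all fall on Days -7 to -4, or Visit 2 may land in a natural gap. This stands: a reader might infer that every steady opioid user becomes a non-responder, but 57% or 29% of fixed patterns stay *no change*, and 36–39% of random users escape *increase*. Likewise the 75% is a ratio of expectations. At one or two fixed doses the apparent change is 0%, +100% or undefined.

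Second, much of the misclassification comes from the 15% band at low counts. This also stands, and only the added 18 to 24 points belong to the opioid-free days.

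Third, treating a later dose as new after a zero baseline is one reading, since 2.2.14 defines neither a new drug nor one taken at Baseline. The point stands, but it does not remove the problem. If the drug counts as taken at Baseline, 15% of zero is zero, and any Week 12 use is still an *increase*.

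Fourth, the blinded manual review could spot the artefact. It may, but it is supportive and does not replace the programmed category.

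Fifth, the endpoint is secondary with descriptive P values. That limits the weight of the point without removing the bias from the reported rates.

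**Conclusion.** The point holds in a limited form. The two windows overlap, the opioid reference dose is biased downward, nothing in 2.2.14 corrects it, and an *increase* means non-response. Under the assumed rates, the washout adds about 18 to 24 points to the share of unchanged users classed *increase*. On the alternative reading of a new drug, the addition at one dose a week is nearer 12.

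A reader might infer that the bias favours one arm or touches the trial's main conclusion. The documents do not support either. The rule is the same in both arms, so its main effect is to lower and blur the response rates. The primary endpoint and the 30% and 50% improvement endpoints do not use 2.2.14, and analgesics other than short-acting opioids are not subject to the 3-day rule. The overall effect cannot be sized because the number of opioid users is not given. With 10% to 30% users, as an illustration, the responder difference would shrink by roughly 2% to 8% of itself. This is a minor but real flaw that is cheap to correct.

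**What to change.** Amend SAP 2.2.14 before unblinding and leave the entry rule as it is.

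1. For short-acting opioids only, compute the baseline average daily dose over the 7 eDiary days before the restricted days (Days -10 to -4). Where screening was shorter, use the diary days that exist before Day -3 (at least Days -7 to -4) and divide by their number. Keep the 7-day window for other analgesics.
2. Count a short-acting opioid as new only if neither the screening eDiary nor the 30-day pre-screening medication record (Protocol 8.11.1) shows use.
3. State the Week 12 averaging window, and how a known user with a zero baseline average is judged.

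Feasibility: the diary starts at Screening Visit 1, nominally Day -14, and the minimum screening period is 7 days. Days -7 to -4 therefore exist by design, and usually more.

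Effect: the expected ratio returns to 1.00. Random users return to the no-washout rates for *increase* (46% at 1 dose a week, 39% at 2). A fixed weekly pattern reads *no change*, because any 7 consecutive days contain each weekday once.

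Cost: a few sentences and no new data collection, though item 2 brings in the medication record alongside the diary. With only 4 baseline days the classification is noisier. *Increase* falls from 64% to 56% at 1 dose a week and from 61% to 40% at 2, but false *decrease* rises from 18–20% to 36–39%. The full 7-day window has a similar rate (34–38%). For a truly unchanged user, *decrease* in place of *no change* leaves responder status as it was, but it does distort the category counts. Neither version cures the 15% band's instability at one or two doses a week, so the blinded manual review should stay as the supportive check.
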